5.5 End of Study (EOS)

EOS is defined as 12 months (-14 days, +28 days) after baseline.

If a subject does not attend visit 13, a stepwise approach to obtaining weight will be implemented according to the following hierarchy:

1. Subject called into office for month 12 weight measurement (-14 days, +28 days from scheduled month 12/visit 13).
2. Recent (-14 days, +28 days from scheduled month 12/visit 13) weight extracted from the electronic medical record (EMR).

3. Recent (-14 days, +28 days from scheduled month 12/visit 13) subject-reported weight used.

5.6 Pharmacy Data

In addition to prospectively collected clinical data and PROs, this study will also collect prescription fill data for obesity medication from randomization through EOS.

5.7 Withdrawals

5.7.1 Study Site

The Sponsor and/or the Institutional Review Board (IRB) reserves the right to terminate participation of the study site at any time. The study site may also be terminated for cause per contractual agreement. In such cases, all data collection will end. After the collected data are received, the study clinicians will be compensated as contractually agreed.

5.7.2 Subjects

Participation in the study is voluntary, and all subjects are free to withdraw his/her consent at any time. A subject will only be withdrawn from the study if he/she withdraws consent. In the event of study withdrawal, the study clinician will record the reason for study withdrawal and continue to follow-up with the subject as medically indicated for any unresolved SAEs or pregnancies, if subject agrees. Upon subject consent withdrawal from the study, all data collection will end, but all study data collected up to withdrawal will be included in the study database.

6 STATISTICAL METHODS

6.1 Analysis Overview

Subjects will be randomized 1:1 to WMP + Rx or WMP alone. The data analyses for this study will be outlined in further detail in a Statistical Analysis Plan (SAP).

The significance level used in all statistical analyses will be 5% (two-sided).

6.1.1 Estimands

Two estimands, each targeting a unique research question, have been defined to adequately describe the effect of an employer-based WMP combined with obesity medication compared to an employer-based WMP alone.

Primary estimand

The primary estimand for all endpoints is an “intention-to-treat” estimand (also known as an “effectiveness” or a “treatment policy” estimand). This estimand will quantify the average treatment effect of an employer-based WMP combined with medication for chronic weight

management compared to the employer-based WMP alone after 12 months, in all randomized subjects and regardless of adherence to randomized treatment.

Secondary estimand

The secondary estimand for body weight loss, categorical weight loss, and PROs is an “if all subjects had adhered” estimand (also known as an “efficacy” estimand). This estimand will quantify the average treatment effect of an employer-based WMP combined with medication for chronic weight management compared to the employer-based WMP alone after 12 months, in all randomized subjects had they adhered to their randomized treatment for the entire planned study duration as defined in Section 6.4.3.

6.1.2 Primary Endpoint and Confirming Hypothesis

The primary endpoint is percent change in body weight from baseline (month 0) to month 12 (visit 13), as defined:

$$\% \text{ weight change} = \frac{\text{body weight at visit 13} - \text{body weight at baseline}}{\text{body weight at baseline}} \times 100\%$$

where a negative value indicates a body weight loss from baseline (month 0) to month 12 (visit 13).

One confirmatory hypothesis will be tested:

- Superiority of WMP + Rx versus WMP alone on % weight change from baseline (month 0) to month 12 (visit 13).

The test will be evaluated as a two-sided test of the null hypothesis that the mean weight change (%) in the two treatment arms is the same (H_0 : % weight change [WMP + Rx] = % weight change [WMP]). Superiority will be claimed if the two-sided p-value is less than 5% and the estimated difference in mean weight change favors WMP + Rx (H_a : % weight change [WMP + Rx] < % weight change [WMP]).

6.2 Study Populations

The following analysis sets will be defined:

Full analysis set (FAS): Includes all randomized subjects analyzed according to the treatment group to which they were assigned at randomization.

6.3 Sample Size Determination

6.3.1 Power and Sample Size for Primary Objective

Assumptions for sample size calculations included:

- Two sample two sided t-test with equal variances
- 5% significance level, but superiority is only claimed if estimated difference in mean weight loss favors WMP + Rx (this corresponds to a one-sided test on a 2.5% significance level).
- 1:1 randomization
- 50% of subjects in both arms are expected to drop out (based on input from the Cleveland Clinic)
 - Among subjects who drop out, 50% are expected to return for a month 12 (visit 13) assessment (retrieved drop outs).
 - Retrieved and non-retrieved drop outs in the WMP arm are assumed to have the same effect as subjects who complete the WMP arm.
 - Non-retrieved drop outs in the WMP + Rx arm are assumed to have an effect corresponding to subjects in the WMP arm.
 - Retrieved drop outs in the WMP + Rx arm are assumed to have an effect corresponding to half the weight loss difference (compared to WMP) of subjects who complete the study in the WMP + Rx arm.
- The following expected distribution of prescriptions in the WMP + Rx arm (based on input from the Cleveland Clinic):
 - 0% Orlistat (Xenical®)
 - 10% Lorcaserin/Lorcaserin extended-release (Belviq®/BelviqXR)
 - 30% Phentermine/Topiramate extended-release (Qsymia®)
 - 30% Naltrexone/Bupropion extended-release (Contrave®)
 - 30% Liraglutide 3.0 mg (Saxenda®)

Table 6-1 presents several sample size scenarios and power calculations based on the above assumptions, varying expected mean differences in weight loss between treatment arms (treatment effect) over 1 year and standard deviations (SD) as the variation of weight loss between subjects within the same treatment arm. Treatment effect scenarios of 3, 3.5, 4, and 5% were chosen based on product labels. SD of 8, 9, 10, and 11 % were chosen based on the NN8022 (SCALE) program [18] [19] [20] and the TRAMOMTANA [21] study.

Table 6-1. Power calculations for selected total N, treatment effects, and standard deviations

	Treatment effect (%)															
	3				3.5				4				5			
	SD (%)				SD (%)				SD (%)				SD (%)			
Total N	8	9	10	11	8	9	10	11	8	9	10	11	8	9	10	11
160	0.65	0.55	0.47	0.40	0.79	0.69	0.59	0.52	0.88	0.80	0.71	0.63	0.98	0.94	0.88	0.82
180	0.71	0.60	0.52	0.44	0.83	0.74	0.65	0.56	0.92	0.84	0.76	0.68	0.99	0.96	0.92	0.86
200	0.75	0.65	0.56	0.48	0.87	0.78	0.69	0.61	0.94	0.88	0.80	0.73	0.99	0.97	0.94	0.89
240	0.82	0.73	0.64	0.56	0.92	0.85	0.77	0.69	0.97	0.93	0.87	0.80	1.00	0.99	0.97	0.94
300	0.90	0.82	0.74	0.65	0.97	0.92	0.86	0.78	0.99	0.97	0.93	0.88	1.00	1.00	0.99	0.98

Total N = sum of subjects in both treatment arms; treatment effect = difference in one-year weight loss of WMP + Rx compared to WMP alone; standard deviation (SD) = variation in weight loss between subjects within the same treatment arm.

Based on the above mentioned assumptions and results from the referenced studies, a 4% treatment effect and 10% SD is a conservative, yet realistic scenario. Therefore, a total sample size of 200 subjects (100 subjects per treatment arm) with 80% power for the confirmatory hypothesis assuming a 25% attrition rate over 12 months was chosen.

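### The 80% power at N=200 is that of a t-test on fully observed data; with 25% imputed as specified it is about 71–75% unless baseline weight explains some 10–16% of the variance

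*Protocol*

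**What the plan says.** Protocol section 6.3.1 plans on a two-sample, two-sided t-test at 5% with 1:1 allocation. It also lists drop-out assumptions:

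- "50% of subjects in both arms are expected to drop out", and half of these return for the month 12 weight.
- WMP drop-outs do as well as WMP completers.
- Retrieved WMP + Rx drop-outs keep "half the weight loss difference (compared to WMP) of subjects who complete the study in the WMP + Rx arm".
- "Non-retrieved drop outs in the WMP + Rx arm are assumed to have an effect corresponding to subjects in the WMP arm".

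A further bullet begins "The following expected distribution of prescriptions in the WMP + Rx arm" and gives percentages by drug. The section then says "Table 6-1 presents several sample size scenarios and power calculations based on the above assumptions". The columns of that table are described as "varying expected mean differences in weight loss between treatment arms (treatment effect) over 1 year", together with the SD. It adds: "Treatment effect scenarios of 3, 3.5, 4, and 5% were chosen based on product labels". The 4% and SD 10 scenario is selected with a reference back to the listed assumptions, and a sample of 200 "with 80% power for the confirmatory hypothesis assuming a 25% attrition rate over 12 months was chosen". The synopsis gives the 80% without the attrition condition.

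The primary analysis is set out in Protocol sections 6.4 and 6.4.1 and SAP sections 5.5.1 and 5.6.1. Missing visit 13 weights in both arms are imputed 100 times from a regression fitted to observed WMP subjects only: weight in kg on sex, BMI category and baseline weight. Percent change is then analysed by ANCOVA with baseline weight as covariate, and the results are pooled by Rubin's formula. The SAP text has no sample-size section.

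**The concern.** The power is attached to the confirmatory hypothesis and to a 25% attrition rate, so a reader takes it as the power of the primary analysis with a quarter of the month 12 weights missing. Table 6-1 neither imputes nor removes anyone. Two things are left open: whether 4% is an effect in completers or in all randomized subjects, and what the imputation and pooling do to the power. The first can be inferred from the text. The second cannot, and it lowers the figure even when the first is resolved in the plan's favour. What is at stake is the accuracy of the stated power, not the validity of the test.

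**Working it through.** **1. Reproduce the plan's figure.** Inputs from section 6.3.1: 100 per arm, difference 4, SD 10, two-sided 5%.

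- SE = 10 × √(2/100) = 1.41, and 4/1.41 = 2.83.
- Power is 0.804 by the noncentral t (0.807 by the normal approximation), against 0.80 printed.
- All 80 cells of Table 6-1 reproduce in the same way, using the full N and the column effect and SD. The largest difference is 0.005.

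Attrition does not act through N: 75 per arm gives 0.68. It can act only through the effect column.

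**2. What the 4% must mean.** With the protocol's own weights:

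- Net effect = completer effect × (0.50 × 1 + 0.25 × 0.5 + 0.25 × 0) = 0.625 × completer effect.
- If the columns 3, 3.5, 4 and 5% are net, the completer effects are 4.8, 5.6, 6.4 and 8.0%.

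The 25% is the share not retrieved: 0.50 × 0.50, matching 150 of 200 expected to complete in Protocol section 4.2.5.

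**3. Power of the specified analysis on the net reading.** The SAP analysis was simulated with a 6.4% completer effect, N=200, 25% imputed and a total within-arm SD of 10. R-squared is the share of variance in percent change explained by baseline weight.

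| R-squared | kg imputation model (SAP) | Imputation on the % scale, for range |
|---|---|---|
| 0 | 0.710 | 0.748 |
| 0.05 | 0.735 | 0.773 |
| 0.10 | 0.764 | – |
| 0.15 | 0.794 | 0.823 |
| 0.20 | 0.821 | – |

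There were 12,000 trials per kg entry (Monte Carlo SE about 0.4 points) and 8,000 per %-scale entry. By interpolation, 80% is reached at:

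- kg model: 0.15 + 0.05 × (0.800 − 0.794)/(0.821 − 0.794) = 0.16.
- % scale: 0.05 + 0.10 × (0.800 − 0.773)/(0.823 − 0.773) = 0.10.

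A smaller run (3,000 trials) at R-squared 0.25 gave 0.84 and 0.86.

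**4. Why power is lost.** With a quarter of the WMP + Rx arm set to the WMP level, the estimate is roughly 0.75 × (observed WMP + Rx mean − observed WMP mean).

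- Its expectation is 0.75 × (50 × 6.4 + 25 × 3.2)/75 = 4.0, so the target is unchanged.
- Its SD is about 0.75 × 10 × √(2/75) = 1.22 (1.25 in the simulation at R-squared 0).
- The mean Rubin-pooled SE in that simulation is 1.66, above both this SD and the t-test's 1.41.

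The test therefore divides by too large an SE. A rough check: (4 − 1.96 × 1.66)/1.25 = 0.60, which gives power of about 0.72, in line with the simulated 0.71. With no effect, 1.96 × 1.66/1.25 = 2.60, a one-sided rejection rate of about 0.5%. The simulation also gives 0.5%, against 2.5% nominal.

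**5. The N=200, SD 10 row (net reading, kg model).**

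| Effect | 3% | 3.5% | 4% | 5% |
|---|---|---|---|---|
| Printed | 0.56 | 0.69 | 0.80 | 0.94 |
| R-squared 0 | 0.42 | 0.57 | 0.71 | 0.91 |
| R-squared 0.15 | 0.49 | 0.66 | 0.79 | 0.95 |

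**Assumptions not in the documents:** R-squared; 25% male; BMI of 30 plus a gamma variable with mean 7; WMP mean change of −5%; missingness completely at random. Varying the sex mix (10–50% male), gamma mean (5–10) and WMP change (−2 to −8%) moves the kg result only within 0.71–0.73 at R-squared 0 and 0.79–0.81 at 0.15.

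**The case against.** The sponsor can say that the table has no arithmetic error, that section 6.3.1 openly names a t-test, and that planning on a t-test and analysing by ANCOVA is common and usually safe, because the covariate adds power. Much of this stands. With a predictive enough baseline weight, the specified analysis meets or exceeds 80%. But the usual safety margin is partly or wholly used up here by reference-based imputation with Rubin pooling, and the plan relies on a covariate gain that it does not state. The 25% is also the plan's figure for subjects without an on-site weight. The fallback steps in Protocol section 5.5 (medical record, then self-report) could leave fewer values to impute and so a smaller shortfall.

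Three stronger readings are tempting, and the documents do not support them.

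- *True power is 42%.* This takes 4% as a completer effect, so the net effect is 0.625 × 4 = 2.5% and the t-test gives 0.42 (the specified analysis about 0.27–0.36 over R-squared 0–0.15). The reference to product labels leaves room for it. But the table and the 4% are both said to follow from the listed assumptions, the effect is defined as a difference between arms, the estimand covers all randomized subjects, and the zero-effect bullet matches the WMP-arm imputation. On the completer reading, the drop-out bullets would have no function.
- *N should have been inflated for 25% attrition.* Subjects without a month 12 weight stay in the full analysis set with imputed values, so using all 200 is consistent. The 0.68 at 75 per arm shows only that attrition was not taken out of N.
- *The power claim cannot be checked.* Every cell can be. Only the step from label effects to 4% is missing.

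**Conclusion.** The concern holds in a limited form. The 0.80 is correct for a t-test on 200 fully observed subjects with a net effect of 4% and SD 10. It is not the power of the specified analysis with 25% imputed. That power is about 71–75% at R-squared 0, about 79–82% at 0.15, and 80% at about 0.10–0.16. This takes the better supported net reading and rests on the assumed R-squared and on 25% of weights being imputed. The shortfall is at most about 9 points and disappears if baseline weight is predictive enough. Type I error is not inflated, since the test is conservative, and the estimand is unaffected. Whether 6.4% in completers is realistic cannot be judged from the documents, which do not give the label effects.

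**What to change.** In Protocol section 6.3.1, without adding patients:

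1. Recompute the chosen N=200 row for the specified primary analysis with 25% imputed, and state the covariate strength assumed. Restate the power in 6.3.1 and the synopsis accordingly.
2. In the same edit, say that the 3, 3.5, 4 and 5% effects are net of drop-out, and give the implied completer effects (4.8, 5.6, 6.4 and 8.0%). If they are in fact completer effects, apply the 0.625 factor before computing power.

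The cost is a few sentences and one table row. The downside is that the stated power becomes somewhat less favourable, unless an R-squared of about 0.10–0.16 or more can be justified. Conduct, sample size and analysis stay as they are.

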6.3.2 Interim Analysis

There is no interim analysis planned for this study.

6.4 Primary Estimand for the Primary Endpoint

The primary estimand will be estimated based on the FAS and % weight change will be modeled using linear regression (Analysis of Covariance (ANCOVA)) with randomized treatment as a factor and baseline body weight (kg) as a covariate. The treatment difference between WMP + Rx and WMP alone will be estimated and reported together with the associated 95% confidence interval (CI) and corresponding p-value.

6.4.1 Primary Estimand Missing Data Imputation

Prior to analysis, missing month 12 weight data will be imputed by multiple imputations. For the primary analysis, missing month 12 weight data will be imputed by sampling among all available assessments at visit 13 in the WMP arm (including values from retrieved drop outs). This approach is also known as “jump to reference” and makes the assumption that subjects instantly lose any effect of randomized treatment beyond what can be expected from the WMP after

discontinuation. Body weight measurements at visits between baseline (month 0) and month 12 (visit 13) are not used for this imputation approach. Imputation details will be further described in the SAP.

6.4.2 Sensitivity Analysis of the Primary Estimand for the Primary Endpoint

A multiple imputation approach as described by McEvoy [22] will be used as sensitivity analysis. In this approach, month 12 measurements at visit 13 for non-retrieved drop outs will be imputed by sampling from values obtained from retrieved drop outs in the corresponding treatment arm and according to the timing of last available body weight. If this approach is not feasible, no sensitivity analysis will be done.

6.4.3 Secondary Estimand for the Primary Endpoint

The secondary estimand of the primary endpoint will address the efficacy of medication for chronic weight management if all subjects adhere to their randomized treatment (WMP + Rx or WMP). For the secondary estimand, the primary endpoint will be analyzed using a mixed model for repeated measurements (MMRM) including all subjects, but for subjects considered non-adherent to randomized treatment, only data prior to non-adherence will be used. Month 12 (visit 13) assessments for retrieved drop outs will not be used in this analysis. The MMRM for efficacy will only use assessments from subjects who are adherent to the randomized treatment until end of treatment, or up until the subject is considered non-adherent to the randomized treatment. Subjects in the WMP arm will be considered non-adherent if/when criterion 1 below is met. Subjects in the WMP + Rx arm will be considered non-adherent if/when criterion 1 or 2 is met:

1. Missing 4 SMA visits. In this case, the last assessment made prior to the 4th missed SMA visit will be used as the last assessment. This is also the case if, e.g., 4 SMA visits in a row are missed.
2. Period with no coverage of prescription claims according to PDC exceeds 20% of planned medication duration, or number of days from visit 1 to visit 13. For subjects that drop out early, the expected visit 13 date (derived from the subjects' planned SMA group visit) will be used to calculate planned study duration. The last assessment made prior to exceeding 20% of planned study duration with no prescription claims will be used as last assessment.

The MMRM for efficacy will be fitted using % weight change with randomized treatment as factor and baseline body weight (kg) as covariate, all nested within visit. An unstructured covariance matrix for measurements within the same subject will be employed, assuming that measurements for different subjects are independent.

6.4.4 Supplementary Analyses

The analyses of % weight change will be supplemented with a completer analysis based on the subset of subjects with month 12 (visit 13) body weight data who were adherent to the randomized treatment.

Completer analysis

In the context of this supplementary analysis, completers will be defined as subjects with month 12 (visit 13) body weight data who adhered to randomized treatment up to and including visit 13. Adherence is defined as for the secondary estimand for the primary endpoint in section 6.4.3, i.e., subjects in the WMP arm will be considered non-adherent if/when criterion 1 above is met and subjects in the WMP + Rx arm will be considered non-adherent if/when either criterion 1 or 2 above is met. As an example, a subject in the WMP + Rx arm that misses visit 10, 11, and 12, but attends all other visits and is covered by prescription claims for at least 80% of the planned study duration, is considered a completer in this context if month 12 (visit 13) weight data are available.

This analysis will use the same ANCOVA model described for the primary estimand analysis of the primary endpoint (section 6.4).

6.5 Primary Estimand for the Secondary Endpoints

The following analyses are planned to further support the primary objective to compare weight loss of WMP + Rx versus WMP. They will also address the secondary objectives of this study to compare WMP + Rx versus WMP with respect to categorical weight loss, WMP adherence, and PROs, as well as adherence to obesity medication within the WMP + Rx cohort.

All secondary analyses described in this section will be the primary estimand based on the FAS. No sensitivity analyses are planned for the secondary endpoints.

6.5.1 Categorical Weight Loss

For the categorical weight loss endpoints ($\geq 5\%$ weight reduction from baseline, $\geq 10\%$ weight reduction from baseline), the proportion of subjects achieving each endpoint will be analyzed using a logistic regression model with treatment as categorical effect and baseline weight (kg) as covariate. From the model, the estimated odds ratio (OR) (WMP + Rx / WMP) will be presented with the 95% CI and p-value. An OR above 1 favors WMP + Rx. Missing weight data will be imputed as described for the primary estimand for the primary endpoint (section 6.4.1).

6.5.2 Adherence to Weight Management Program (WMP)

WMP adherence will be assessed through SMA attendance endpoints. SMA attendance will be reported as the percentage planned SMAs attended, i.e., number of SMAs attended/12 planned SMAs. SMA attendance and the proportion of subjects achieving ≥ 9 SMAs will be descriptively summarized by treatment arm. No formal statistical testing will be conducted.

6.5.3 Adherence to Obesity Medication

Adherence to obesity medication will be assessed through PDC (to be defined in the SAP) for the WMP + Rx treatment arm only. The PDC and the proportion of subjects with at least 80% PDC will be descriptively summarized for the WMP + Rx treatment arm. No formal statistical testing will be conducted.

6.5.4 Patient Reported Outcome (PRO) Analysis

Work productivity and work limitations will be assessed by the WPAI:SHP and WLQ-8 instruments (section 5.3.1). Analysis of change from baseline (month 0) to month 12 (visit 13) in work productivity and work limitation endpoints defined in section 3.2 will follow the method described for the primary estimand for the primary endpoint: ANCOVA model with randomized treatment as a factor and baseline value of the endpoint variable as covariate. Estimated difference (WMP + Rx minus WMP) in change from baseline (month 0) to month 12 (visit 13) will be presented with 95% CI and corresponding p-value. If examination of the data indicate that it is not justifiable to model data based on assumptions of normality, e.g., many responses of 0% or close to 0%, alternative statistical modeling will be used (e.g. logistic regression after definition of a responder limit).

